### **Follow-up period**

The 4-week wash out period will monitor the safety and tolerability profile after the last dose of study drug.

The investigator must provide appropriate advice on the continued use of effective contraception for at least one week (at least 5 half-lives of QAW039) after the last dose of study drug and follow up with the subject as appropriate.

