## 5.6 Study completion and discontinuation

### 5.6.1 Study completion and post-study treatment

Study completion for a patient will occur after he/she has completed 12 weeks of treatment (through to Visit 299) or has prematurely withdrawn. Completion of the study will be when

all randomized patients have completed 12 weeks of treatment and the post-treatment Follow-up visit.

Patients who have been screened when enrolment target has been met will be allowed to proceed onto study participation.

A Safety Study of QAW039 is planned. At sites participating in the Safety Study, patients who successfully complete 12 weeks of treatment in this study (Study A2316) may be offered participation in the Safety Study; patient participation in the Safety Study will be optional. Patients not entering the Safety study will complete the follow-up period and will not be given further access to study drug because the risk/benefit ratio will not yet have been substantiated and there are already other marketed therapeutic alternatives available to treat these patients. At the time of study completion or early termination, all patients will be placed on the appropriate asthma treatment as prescribed by the investigator.

The investigator must provide appropriate advice on the continued use of effective contraception for at least one week (at least 5 half-lives of QAW039) after the study completion visit (Visit 299) or premature study drug discontinuation and must follow up with the subject as appropriate at least to the end of this period.

The investigator must provide follow-up medical care for all patients who are prematurely withdrawn from the study, or must refer them for appropriate ongoing care.

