**Table 6-1 Assessment schedule**

Period	Screen	Placebo Run-in		Treatment						Follow-up	Notes
		101	199	201	202	203	204	TD	299		
Visit Number (Site visits)	1	101	199	201	202	203	204	TD	299	301	Follow-up Visit 301 is only applicable for patients not participating in the safety study.
Treatment Week	-3	-1	0	0	2	4	8	TD	12	16	Visit 199 and Visit 201 occur on the same day.
Treatment Day	-21	-7	1	1	14	28	56		84	112	
Informed consent and assent (if applicable)	X										ICF must be obtained within 14 days of Visit 1 or at Visit 1.
Ask question on withholding of medication before clinic visits	S		S		S	S	S	S	S		If the patient has not withheld medications as specified in the protocol before a particular visit, the visit must be rescheduled.
Demographics	X										
Medical history	X										
Medical History – Protocol solicited events for asthma	X										
Asthma exacerbation history	X										
Smoking history	X										
Prior/concomitant medication (asthma and non-asthma medications) review	X		X		X	X	X	X	X		
Inclusion/exclusion criteria	X		X								
Review and record surgeries and procedures	X		X		X	X	X	X	X		
Physical examination	S							S	S		
Abbreviated physical examination			S		S	S	S				Heart and lungs only.
ACQ-5 in clinic			X								
AQLQ+12 in clinic			X			X		X	X		

[figure not shown]
Period	Screen	Placebo Run-in		Treatment						Follow-up	Notes
Visit Number (Site visits)	1	101	199	201	202	203	204	TD	299	301	Follow-up Visit 301 is only applicable for patients not participating in the safety study.
Treatment Week	-3	-1	0	0	2	4	8	TD	12	16	Visit 199 and Visit 201 occur on the same day.
Treatment Day	-21	-7	1	1	14	28	56		84	112	
Train patient and assess patient's ability to use eDiary/ePEF and dispense eDiary/ePEF	S										
Review eDiary /ePEF compliance		S	S †								† eDiary/ePEF compliance must be assessed prior to randomizing the patient.
Review eDiary/ePEF entries		S	S		S	S	S	S	S		
Height	X							X	X		
Weight	X		X					X	X		
Vital signs	X	X	X		X	X	X	X	X		Systolic/diastolic blood pressure, radial pulse (sitting), and body temperature.
Electrocardiogram	X							X			
Electrocardiogram (Pre-dose)				X					X		
Pregnancy test—serum (women of child bearing potential)	X										Pregnancy testing will begin at the visit a patient is first identified as being of child bearing potential. If positive, the patient must not be randomized.

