Reversibility test (spirometry after administration of short-acting $\beta$ -agonist [SABA])	X**	X <math>\alpha</math>,<math>\beta</math>**									
¤To be performed prior to in-clinic witnessed study drug administration.
 
£To be performed after the second (-15 min.) pre-dose spirometry (may be performed after 10 AM <math>\pm</math> 1 h).
 
**If reversibility is NOT demonstrated at Visit 1, reversibility will be attempted at Visit 101. If not achieved, then one additional attempt allowed within 4 days following Visit 101.

Review Visit 1 or Visit 101 or the one additional attempt reversibility result from overread			S								
Asthma exacerbation monitoring	X	X	X	X	X	X	X	X	X	X	In case of an asthma exacerbation, the patient should be encouraged by the site to contact it for advice. If necessary, an unscheduled visit to the site may be arranged.
Serious adverse event monitoring	X	X	X	X	X	X	X	X	X	X	
Adverse event monitoring	X	X	X	X	X	X	X	X	X		
Liver event monitoring	X	X	X	X	X	X	X	X	X	X	If applicable, review lab results and clinical events as per Section 7.3 .
Renal event monitoring	X			X				X	X		If applicable, review lab results as per Section 7.4 .

Period	Screen	Placebo Run-in		Treatment						Follow-up	Notes
Visit Number (Site visits)	1	101	199	201	202	203	204	TD	299	301	Follow-up Visit 301 is only applicable for patients not participating in the safety study.
Treatment Week	-3	-1	0	0	2	4	8	TD	12	16	Visit 199 and Visit 201 occur on the same day.
Treatment Day	-21	-7	1	1	14	28	56		84	112	
Record deaths	X	X	X	X	X	X	X	X	X	X	
Contact IRT	S	S	S	S	S	S	S	S	S	S	
Randomize patient through IRT				S							
Assess and dispense rescue SABA to be used on an as-needed basis	S*	S	S	S	S	S	S	S	S**		*dispense SABA only **assess SABA only
Dispense study drug		S		S	S	S	S				Patients will be instructed to take study drug in the morning.
Assess compliance with study drug (count tablets in returned bottles)			S		S	S	S	S	S		
In-clinic witnessed study drug intake		X		X	X	X	X		X		Complete Dosage Administration Record (DAR)-Visit – at site visit.
Complete Study Drug Dosage Administration Record-Summary page			X		X	X	X	X	X		Complete DAR- Summary at each indicated visit to record compliance
Complete Study Disposition page (screening)	X										
Complete Study Disposition page (run-in)			X								
Complete Study Disposition page (end of treatment )									X		

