## 7 Safety monitoring

### 7.1 Adverse events

An adverse event (AE) is any untoward medical occurrence (e.g., any unfavorable and unintended sign [including abnormal laboratory findings], symptom or disease) in a subject or clinical investigation subject *after providing written informed consent* for participation in the study until the end of study visit. Therefore, an AE may or may not be temporally or causally associated with the use of a medicinal (investigational) product.

In addition, all reports of intentional misuse and abuse of the product are also considered an adverse event irrespective if a clinical event has occurred.

The occurrence of adverse events must be sought by non-directive questioning of the patient at each visit during the study. Adverse events also may be detected when they are volunteered by the patient during or between visits or through physical examination findings, laboratory test findings, or other assessments.

Abnormal laboratory values or test results constitute adverse events only if they fulfill at least one of the following criteria:

- they induce clinical signs or symptoms,
- they are considered clinically significant,
- they require therapy.

Clinically significant abnormal laboratory values or test results must be identified through a review of values outside of normal ranges/clinically notable ranges, significant changes from baseline or the previous visit, or values which are considered to be non-typical in patient with underlying disease. Investigators have the responsibility for managing the safety of individual patient and identifying adverse events. Alert ranges for laboratory and other test abnormalities are included in [Appendix 1](#).

Adverse events must be recorded in the Adverse Events CRF under the signs, symptoms or diagnosis associated with them, accompanied by the following information:

- The severity grade:
  - mild: usually transient in nature and generally not interfering with normal activities
  - moderate: sufficiently discomforting to interfere with normal activities
  - severe: prevents normal activities
- its relationship to the study treatment
  - Yes
  - No
- its duration (start and end dates) or if the event is ongoing an outcome of not recovered/not resolved must be reported.
- whether it constitutes a serious adverse event (SAE - See [Section 7.2](#) for definition of SAE) and which seriousness criteria have been met.
- action taken regarding investigational treatment

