##### **9.5.2.1 Adverse events**

Adverse events after informed consent including asthma exacerbations will be summarized and listed.

Adverse events starting on or after the time of the first intake of study drug will be classified as treatment-emergent adverse events. Any adverse events that started during the study after informed consent before the time of the first intake of study drug will be classified as a prior adverse events and not included in tabulations of treatment emergent adverse events.

The following treatment emergent adverse event summaries will be produced, overall by system organ class and preferred term, overall by system organ class, preferred term and maximum severity, suspected drug-related adverse events by system organ class and preferred term, serious adverse events by system organ class and preferred term, and adverse events leading to permanent discontinuation of study-drug by system organ class and preferred term.

The number and percentage of patients with the most frequent AEs will be summarized by treatment.

Selected adverse events of special interest may be summarized and analyzed as well.

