2.7.1 Adverse events (AEs)

All adverse events, including asthma exacerbations, coded with MedDRA using the most actual version at the time of database lock, will be listed. Unless otherwise specified, summaries will include treatment-emergent adverse events (TEAEs) only. AEs starting on or after the time of the first intake of study drug and not later than 7 days (30 days in the case of a serious AE) after the last intake of study drug will be classified as a TEAE. For those patients who enter the safety study (CQAW039A2315) directly after Visit 299, AEs (including serious AEs) starting after Visit 299 will not be considered as TEAEs in this study as they will be reported in CQAW039A2315.

As a general rule of censoring, patients who either completed the study or discontinue treatment prematurely and without the event of interest will be censored at the minimum out of the dates of last medication intake + 30 days, final visit date, and date of death. The number and percentage of patients who reported TEAEs will be summarized by primary system organ class (SOC), preferred term (PT), and treatment group for

- all adverse events (AEs)
- all AEs by maximum severity
- AEs suspected to be related to study drug
- AEs by standardized MedDRA query (SMQ) level
- serious AEs (SAEs)
- AEs leading to permanent study drug discontinuation
- AEs of special interest

Unless otherwise specified, primary system organ classes will be sorted alphabetically and, within each primary system organ class, the preferred terms will be sorted in descending order of frequency in the QAW039 150 mg once daily treatment group. If a patient reported more than one AE with the same preferred term, the AE will be counted only once. If a patient reported more than one AE within the same primary system organ class, the patient will be counted only once at the system organ class level.

In addition, the most frequent AEs will be presented by preferred term in descending order of frequency in the QAW039 150 mg once daily treatment group.

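### Protocol Table 6-1 leaves adverse event monitoring blank at follow-up Visit 301, contradicting Section 7.1 and the SAP's 7-day post-dose window for non-serious events

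*Protocol*

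**What the plan says.** **Schedule.** Protocol Table 6-1 has ten visit columns. The row for "adverse event monitoring" carries nine marks and is blank at Visit 301. The row for "Serious adverse event monitoring" carries ten, as do the rows for asthma exacerbations, liver events and deaths. The table also notes: "Follow-up Visit 301 is only applicable for patients not participating in the safety study". Protocol Section 6 presents the table as the full list of assessments.

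**Collection rule.** Protocol Section 7.1 requires open questioning about adverse events at every visit, with no exception for Visit 301. It defines the adverse event period as running from consent "until the end of study visit" but does not say which visit that is. Section 5.6.1 sets contraception advice to run for a period "after the study completion visit (Visit 299) or premature study drug discontinuation", so it labels Visit 299 as the completion visit. The same section ties completion of the study as a whole to the follow-up visit.

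**Purpose of follow-up.** Section 3.2 states: "The 4-week wash out period will monitor the safety and tolerability profile". Section 3.1 says the follow-up visit is there to finish the safety assessments.

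**Analysis window.** Protocol 9.5.2.1 sets only a start: "Adverse events starting on or after the time of the first intake of study drug will be classified as treatment-emergent adverse events". SAP 2.7.1 adds the end: "not later than 7 days (30 days in the case of a serious AE) after the last intake of study drug". For patients who go straight into the safety study, SAP 2.7.1 assigns events starting after Visit 299 to that study.

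**The concern.** The SAP opens a 7-day window after the last dose for non-serious events. For a patient who completes treatment, the whole window lies after Visit 299. If the patient does not enter the safety study, the one remaining scheduled visit is 301, where the table does not call for adverse event enquiry.

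Patients who stop drug early are treated differently. Section 5.6.2 makes adverse events part of the minimum data after discontinuation. Section 6 asks that patients who do not return at least be contacted by phone at the planned end of follow-up, with adverse events on the list of questions. Two groups that share one analysis window could therefore be asked about it differently.

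Treatment-emergent adverse events are an endpoint of the fourth secondary objective. At stake is whether their count rests on the same enquiry at every site and for every patient.

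**Working it through.** The plan states no figure to reproduce. The check sets the passages side by side and adds day arithmetic.

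**1. Is the blank cell real?** The tables were read by a program, so the row was counted against the columns. The nine marks fall under Visits 1, 101, 199, 201, 202, 203, 204, TD and 299. The adjacent serious-event row has ten. The counts fit the layout, so the blank does not look like a reading error.

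**2. Where does the window fall?** Inputs: last dose at Week 12 (Protocol 3.2), planned Day 84 (Table 6-1); Visit 301 on planned Day 112 (Table 6-1); 7-day limit (SAP 2.7.1).
- Window for non-serious events after the last dose: Days 85 to 91.
- Visit 301 falls 112 − 84 = 28 days after the last dose.
- Section 6 places safety assessments before the witnessed dose, so the enquiry at Visit 299 comes before that dose.
- For completers outside the safety study, no scheduled visit other than 301 can cover Days 85 to 91.

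**3. Share of at-risk time.** 84 + 7 = 91 days, and 7 / 91 = 7.7%. This is a share of time. The documents give no event rate for the window, so it cannot be turned into a share of events.

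**4. How many patients?** Inputs: 650 randomized and 15% discontinuing study drug (Protocol Section 4).
- Completers: 0.85 × 650 = 552.5, about 553.
- The share r of completers who enter the safety study is not given. The number exposed is 552.5 × (1 − r): about 553 at r = 0, about 276 at r = 0.5, and 0 at r = 1.

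**5. Which events?** Serious events, exacerbations, liver events and deaths are all marked at Visit 301. A moderate exacerbation (Section 6.4.3) can be an outpatient steroid course and need not be serious. What remains exposed is non-serious events that are neither exacerbations nor liver events.

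**6. Does the arm comparison suffer?** Only if discontinuation differs between arms. Suppose it differs by d, nobody rolls over, the whole window goes unasked in completers and early stoppers are fully covered. The gap in covered at-risk time is then roughly d × 7.7%. With d = 0 it is zero. With an assumed 10% against 20%, it is 0.10 × 7.7% = 0.8 percentage points. The documents state no arm difference; the 15% is a single overall assumption.

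**7. Do the texts agree?** Section 7.1 asks at every visit, while the table does not ask at Visit 301. Both cannot be followed literally.

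**The case against.** The strongest reply is that Section 7.1 already governs. It requires questioning at every visit, accepts events volunteered at or between visits, and makes no exception for follow-up. Section 3.1 gives Visit 301 a safety purpose, and Section 5.6.1 counts the follow-up visit towards completion of the study. On this view the blank cell is a slip that a careful site would see through. The SAP limit is also a rule for classifying events, not a promise to collect them.

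Much of this stands. A reader might infer from the table that completers' post-dose non-serious events are lost, or that the SAP window is empty for them. The documents do not support that. Section 7.1 points the other way, non-serious exacerbations and liver events are marked at Visit 301, and events in patients who roll over are reported in the safety study.

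The reply does not remove the contradiction. Section 6 presents the table as complete, so a site may reasonably take a blank cell to mean not done. Section 7.1 ends collection at an undefined visit, and Section 5.6.1 gives some ground for reading that as Visit 299. The fallback in Section 7.1 for later events covers only those thought related to treatment; they go into source documents and reach the sponsor only if serious. Two sites could each claim to follow the protocol and return different data.

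**Conclusion.** The point holds as an internal contradiction that creates a risk of under-collection. Table 6-1 conflicts with Section 7.1, with the stated purpose of the follow-up period, and with the SAP window.

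The exposure is at most 7 of 91 at-risk days (7.7%) per affected patient, in 0 to about 553 of 650 patients. It is confined to non-serious events other than exacerbations and liver events. The upper end assumes 15% discontinuation, no rollover and sites that work from the table alone.

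Unequal ascertainment between arms is conditional on unequal discontinuation. Even under the illustrative 10% against 20% it is small for descriptive safety tables. The point should still be corrected, because the remedy is cheap and changes which safety data are collected.

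**What to change.** Mark the adverse event row at Visit 301 in Table 6-1. In Section 7.1, define the end of study visit as Visit 301 for patients not entering the safety study and as Visit 299 for those who do. The table, Section 7.1 and SAP 2.7.1 would then describe the same collection period.

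The cost is a small protocol amendment, with the approvals set out in Section 11.1, and slightly more data entry at a visit that already takes place and already records serious events. The concomitant medication and procedures rows are also blank at Visit 301, so the sponsor should decide in the same amendment whether they need matching marks.

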## 6.1 Information to be collected on screening failures

All patients who have signed informed consent but have not entered into the placebo run-in period will have the study completion page for the screening period, demographics, inclusion/exclusion, and serious adverse event (SAE) data collected. Adverse events that are not SAEs will be followed by the investigator and collected only in the source data.

All patients who have signed informed consent and have received placebo study medication, but discontinue prior to randomization (run-in failures) must have all data for the visits they attended, the summary pages (adverse event, concomitant medication, dosage administrative record), and screening and placebo run-in disposition pages completed. All adverse events **occurring after informed consent is signed** must be recorded on the Adverse Event eCRF.

## 6.2 Patient demographics/other baseline characteristics

The following demographics and baseline characteristics will be collected on all patients:

- Age
- Gender
- Race and ethnicity
- Height
- Weight
- Body mass index (BMI)
- Duration of asthma
- Number of exacerbations in prior year
- Atopic Yes/No (RAST/ImmunoCap)
- Smoking history
- Reversibility (demonstrated)
- FEV1
- [REDACTED]
- Baseline ACQ-5
- Baseline AQLQ+12
- [REDACTED]
- ICS use alone/ICS plus a second controller
- Relevant medical history/current medical condition present before signing informed consent. Where possible, diagnoses and not symptoms will be recorded.

Investigators will have the discretion to record abnormal test findings on the medical history CRF whenever in their judgment the test abnormality occurred prior to the informed consent signature.

## 6.3 Treatment exposure and compliance

Study drug compliance will be assessed by the investigator and/or study personnel at designated visits by recording tablet counts from the previously dispensed bottles. This

information must be captured in the source document at each visit. All study drug dispensed and returned must be recorded in the Drug Accountability Log.

Start and end dates of doses of study drug administered since the last dispensing visit will be recorded in the eCRFs (study drug dosage administration record (DAR)-summary page) at visits specified in the table of assessments (Table 6-1).

All doses of study drug taken at the clinic visits must be from the newly assigned medication bottles, **except at Visit 299 when the medication returned by the patient should be used.**

## 6.4 Efficacy

### 6.4.1 Spirometry (Pre-dose FEV1 [REDACTED])

All clinic visits must occur in the morning. Please refer to Section 6 and Table 6-1 for full details of the scheduling of spirometry measurements.

Equipment for spirometry assessments will be provided to all study sites by a Central Spirometry vendor, and overread of spirometry assessments will be performed by trained spirometry technicians at the central vendor.

Please refer to the Spirometry Guidance, in Appendix 5 (Spirometry Guidance), for full details on scheduling and performing spirometry. Reversibility testing must be conducted in the morning.

### 6.4.2 eDiary for daily asthma symptoms, [REDACTED] and rescue medication use

The study will use the asthma diary reported by Santanello et al (1997). This asthma diary was validated in studies of patients aged 18 to 65 years (Santanello et al. 1997). The diary was subsequently included as a measure in placebo-controlled studies of montelukast in patients aged 15 years and older (Reiss et al. 1998, Malmstrom et al. 1999) and shown to be responsive to both montelukast and inhaled beclomethasone therapy in this age range. **All patients will complete the asthma diary regardless of age.**

All patients will be provided with a patient electronic diary (referred to as eDiary or eDiary/ePEF) to record daily asthma symptoms, [REDACTED], and SABA (salbutamol/albuterol) use. Patients will be instructed to routinely complete the patient diary twice daily – at the same time each morning and each evening, approximately 12 hours apart. The eDiary/ePEF recordings are to be reviewed at each clinic visit as detailed in Table 6-1 until study completion. Sites and patients will receive appropriate training and guidance on the use of the eDiary/ePEF device.

The information detailed below will be collected in the eDiary/ePEF. Daytime asthma symptoms will be rated on a 0 to 6 scale and nocturnal asthma symptoms will be rated on a 0 to 3 scale.

